6.2 Toxicity Management

The management of specific AEs and laboratory parameters is described below. This includes AEs of TLS, major hemorrhage, and neutropenia for venetoclax and known potential risks associated with ibrutinib.

Tumor lysis syndrome: There is a potential for TLS in subjects affected by hematologic malignancies. Depending on the specific tumor type, risk factors may include one or more of the following: bulky disease or high tumor burden, renal insufficiency, splenomegaly, elevated pretreatment lactate dehydrogenase levels, elevated leukocyte count, and dehydration.

Venetoclax can cause rapid reduction in tumor and thus poses a risk for TLS. Changes in electrolytes consistent with TLS that require prompt management can occur as early as 6 to 8 hours following the first dose of venetoclax ([Appendix E](#)). Potassium increases can be life-threatening and should be treated as an emergency. Definitions of laboratory TLS and clinical TLS are provided in the [Appendix D](#) (Howard grading classification). Due to the short dose ramp-up used in this study, all subjects will be managed as high risk for TLS. If a subject experiences blood chemistry changes suggestive of TLS, the dose of venetoclax should be withheld and reductions may be required ([Appendix F](#)).

Major hemorrhage: Fatal bleeding events have occurred in patients treated with ibrutinib. A major hemorrhage is any hemorrhagic AE of Grade 3 or higher; any SAE of bleeding of any grade; or any

central nervous system hemorrhage/hematoma of any grade. All hemorrhagic AEs requiring a transfusion of red blood cells should be reported as a Grade 3 or higher per NCI-CTCAE. Ibrutinib may be withheld and/or reductions may be required.

Neutropenia: Venetoclax may cause neutropenia. Subjects with a history of neutropenia who have received multiple prior therapies and/or have significant bone marrow involvement may be at a particularly high risk. Grade 3 or 4 neutropenia has been reported in subjects treated with venetoclax. Subjects will be managed for neutropenia as detailed below.

Known potential risks associated with ibrutinib are listed below, and treatment may be discontinued or adjusted in response to occurrence of these events, as appropriate. Please refer to the ibrutinib Investigator's Brochure⁹ for additional information on potential risks for ibrutinib.

- hemorrhage, infections, cytopenias, cardiac arrhythmias, hypertension, second primary malignancies, and TLS

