Antihyperuricemic agents: Oral uric acid-reducing agent (allopurinol except if contraindicated) should be administered 72 hours before first venetoclax dose to all subjects; rasburicase should be considered prophylactically if the subject's baseline uric acid is elevated, unless contraindicated.

Blood chemistry monitoring: Chemistry and hematology laboratory tests are to be performed upon admission the night before the first dose of venetoclax. The investigator's decision to proceed with venetoclax treatment initiation will be based on these laboratory values. Laboratory monitoring for TLS is to occur at time 0 (predose, within 4 hours before venetoclax administration) and 4, 8, 12, and 24 hours after each dose escalation (including the optional increase to 600 mg at Week 8 or thereafter) on real time (turnaround < 2 hours). A dose increase must not be allowed until the subject's 24-hour laboratory test results have been reviewed by investigator. Results from time 0 (predose) laboratory values will be collected and used as baseline to assess potential electrolyte abnormalities occurring after venetoclax administration. Results from time 0 (predose) on Day 1 are not required to be available prior to initiating venetoclax treatment.

Nephrology consultation: Nephrology (or other acute dialysis service) consultation should be considered upon admission per institutional standards at the investigators' discretion to ensure emergency dialysis is available and the appropriate staff is aware and prepared to handle any necessary intervention for TLS. Telemetry should also be considered.

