APPENDIX D. DEFINITIONS OF LABORATORY AND CLINICAL TUMOR LYSIS SYNDROME

Metabolic Abnormality	Criteria for Classification of Laboratory Tumor Lysis Syndrome	Criteria for Classification of Clinical Tumor Lysis Syndrome
Hyperuricemia	Uric acid > 8.0 mg/dL (475.8 μmol/L) in adults or above the upper limit of the normal range for age in children	
Hyperphosphatemia	Phosphorus > 4.5 mg/dL (1.5 mmol/L) in adults or > 6.5 mg/dL (2.1 mmol/L) in children	
Hyperkalemia	Potassium > 6.0 mmol/liter	Cardiac dysrhythmia or sudden death probably or definitely caused by hyperkalemia
Hypocalcemia	Corrected calcium < 7.0 mg/dL (1.75 mmol/L) or ionized calcium < 1.12 mg/dL (0.3 mmol/L) ^a	Cardiac dysrhythmia, sudden death, seizure, neuromuscular irritability (tetany, paresthesias, muscle twitching, carpopedal spasm, Trousseau's sign, Chvostek's sign, laryngospasm, or bronchospasm), hypotension, or heart failure probably or definitely caused by hypocalcemia
Acute kidney injury ^b	Not applicable	Increase in the serum creatinine level of 0.3 mg/dL (26.5 μmol/L) (or a single value > 1.5 × the upper limit of the age-appropriate normal range if no baseline creatinine measurement is available) or the presence of oliguria, defined as an average urine output < 0.5 mL/kg/hr for 6 hrs

a. The corrected calcium level in mg/dL = measured calcium level in mg/dL + 0.8 × (4-albumin in g/dL).

b. Acute kidney injury is defined as an increase in the creatinine level of at least 0.3 mg/dL (26.5 μmol/L) or a period of oliguria lasting 6 hours or more. By definition, if acute kidney injury is present, the subject has clinical tumor lysis syndrome.

Note: In laboratory tumor lysis syndrome, 2 or more metabolic abnormalities must be present during the same 24-hour period within 3 days before the start of therapy or up to 7 afterward. Clinical tumor lysis syndrome requires the presence of laboratory tumor lysis syndrome plus an increased creatinine level, seizures, cardiac dysrhythmia, or death.

Source: Howard SC, Jones DP, Pui CH. The tumor lysis syndrome. *N Engl J Med.* 2011;364(19):1844-54.

APPENDIX E. RECOMMENDATIONS FOR INITIAL MANAGEMENT OF ELECTROLYTE ABNORMALITIES AND PREVENTION OF TUMOR LYSIS SYNDROME

Abnormality	Management Recommendations
Hyperkalemia (Including Rapidly Rising Potassium)	

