7.3 Analysis of Laboratory Data

Definition of Baseline

The baseline value for laboratory variables will be defined as:

- For subject hospitalized for TLS prophylaxis, the baseline value will be the lab value taken at hospital admission prior to the subject receiving hydration for TLS prophylaxis (the day prior to the first dose of study drug).
- For subject not hospitalized for TLS prophylaxis, the baseline value will be the 0 hour lab draw prior to the first dose of study drug on Day 1.

Laboratory Assessments for TLS

To determine if a subject's laboratory values qualify for TLS, the Howard criteria will be assessed. The Howard definition for laboratory TLS requires ≥ 2 of the metabolic abnormalities specified in [Table 3](#) post-baseline and within 24 hours of each other.

Table 3. Laboratory Criteria for TLS

Element	Value
Uric Acid	> 476 $\mu\text{mol/L}$ (8 mg/dL)
Potassium	> 6.0 mmol/L (6 mEq/L)
Inorganic Phosphorus	> 1.5 mmol/L (4.5 mg/dL)
Calcium	< 1.75 mmol/L (7 mg/dL)

The following summaries of laboratory criteria will be provided:

- Number and percentage of subjects meeting the definition of laboratory TLS (at least two values meeting the criteria in [Table 4](#), occurring within 24 hours of each other).
- Listing of all values for these four analytes for each subject meeting the definition of laboratory TLS at least once during treatment.

Assessment of Drug-Induced Liver Injury

The number and percentage of subjects in each treatment group who have at least one observed post-baseline value meeting the following criteria will be tabulated: ALT > $3 \times \text{ULN}$, AST > $3 \times \text{ULN}$, AST or ALT > $3 \times \text{ULN}$, total bilirubin value > $2 \times \text{ULN}$, ALT or AST > $3 \times \text{ULN}$ and total bilirubin > $2 \times \text{ULN}$ within 24 hours. A listing of all observed ALT, AST, and total bilirubin values will be generated for subjects with an observed value meeting any of these criteria.

Analysis of Shift from Baseline in Clinical Laboratory Data

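### SAP 7.3 calls its laboratory TLS rule Howard but uses uncorrected calcium, where Protocol Appendix D uses albumin-corrected or ionized calcium

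*SAP*

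**What the plan says.** **Protocol.** Section 6.2, in its TLS paragraph, says "Definitions of laboratory TLS and clinical TLS are provided in the" Appendix D, which it identifies as the Howard classification. The calcium criterion there is "Corrected calcium < 7.0 mg/dL (1.75 mmol/L) or ionized calcium < 1.12 mg/dL", and a footnote prints the albumin correction. The note under the table says that two or more "metabolic abnormalities must be present during the same 24-hour period within 3 days before the start of therapy or up to 7 afterward". No unit follows the 7, and the start of therapy is not tied to a study day.

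**SAP.** Section 7.3 says the Howard criteria will be assessed, then states: "The Howard definition for laboratory TLS requires ≥ 2 of the metabolic abnormalities specified in" Table 3, post-baseline and no more than 24 hours apart. The calcium entry is "< 1.75 mmol/L (7 mg/dL"), with no reference to albumin or to ionized calcium. The uric acid, potassium and phosphorus limits agree with Appendix D (475.8 against 476 µmol/L for uric acid is rounding).

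The planned outputs are a count with percentage and a "Listing of all values for these four analytes for each subject" "meeting the definition of laboratory TLS at least once during treatment". The SAP sets no limit relative to the start of therapy. Protocol 6.2 requires TLS draws "after each dose escalation (including the optional increase to 600 mg at Week 8 or thereafter").

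**The concern.** Both documents claim one published definition, but they apply the same calcium number to different quantities. A programmer who follows SAP Table 3 will compare measured calcium with 7 mg/dL at every albumin level, and the result will carry the Howard label. TLS is an adverse event of special interest in Protocol 6.1, and Protocol 6.2 manages every subject as high risk for it, so the rate will be read with care.

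The planned listing would not reveal the difference. It shows the four analytes without albumin, and only for subjects already positive under the SAP rule. A subject positive only under Appendix D would not appear in it.

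**Working it through.** There is no planned figure to reproduce: neither document states an expected TLS rate. The check applies Appendix D's own formula to the SAP's cut-off.

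**Inputs**
- Correction (Appendix D, footnote a): corrected calcium = measured calcium + 0.8 × (4 − albumin), in mg/dL and g/dL.
- Appendix D limit: corrected calcium < 7.0 mg/dL. SAP Table 3 limit: calcium < 7 mg/dL.
- Both rules need at least two abnormal analytes within 24 hours.
- Albumin values are assumptions; the documents give none.

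**Equivalent cut-off.** Corrected < 7.0 is the same as measured < 7.0 − 0.8 × (4 − albumin).

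| Albumin (g/dL) | Appendix D cut-off on measured calcium (mg/dL) | SAP cut-off |
|---|---|---|
| 2.5 | 7.0 − 1.2 = 5.8 | 7.0 |
| 3.0 | 7.0 − 0.8 = 6.2 | 7.0 |
| 3.5 | 7.0 − 0.4 = 6.6 | 7.0 |
| 4.0 | 7.0 | 7.0 |
| 4.5 | 7.0 + 0.4 = 7.4 | 7.0 |

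**When the status changes.** Potassium is 4.5 mmol/L throughout, uric acid is 6 mg/dL unless stated, and no ionized calcium result is available.

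| Case | Calcium, albumin | Corrected | Other values | SAP | Appendix D |
|---|---|---|---|---|---|
| A | 6.5, 2.5 | 7.7 | phosphorus 5.0 | 2 abnormal: TLS | 1: not TLS |
| B | 7.2, 4.5 | 6.8 | phosphorus 5.0 | 1: not TLS | 2: TLS |
| C | 6.5, 2.5 | 7.7 | phosphorus 4.0 | 1: not TLS | 0: not TLS |
| D | 6.5, 2.5 | 7.7 | phosphorus 5.0, uric acid 9 | 3: TLS | 2: TLS |

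Only A and B differ. The calcium rule matters only when exactly one other analyte is abnormal. In case A, an ionized calcium below 1.12 mg/dL would make the subject positive under Appendix D too.

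**Weight of one subject.** 1/14 = 7.1%, 1/31 = 3.2%, 1/34 = 2.9%, 1/37 = 2.7%, taking the Stage 1 and final sample sizes in SAP Table 1 as denominators.

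**Is the correction computable?** Operations Manual 3.12, Table 1, has albumin in the clinical chemistry list but not in the TLS panel. The full panel is required predose at each escalation and the TLS panel at 4, 8, 12 and 24 hours. The 24-hour draw may be the next predose sample, which then carries albumin. The 4, 8 and 12 hour draws need albumin from another sample.

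**Window.** Reading the 7 as days and counting without a Day 0, the Appendix D window closes on Day 7 if therapy starts with ibrutinib (Day −1), or Day 8 if it starts with venetoclax (Day 1). An uninterrupted ramp-up has its draws on Days 1 to 6, inside on either reading. Week 4 Day 1 is Day 3 × 7 + 1 = 22. The earliest 600 mg sampling, at Week 8, is Day 7 × 7 + 1 = 50. Both are outside.

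**The case against.** **The programming plan may supply the correction.** SAP 3.0 leaves conventions to that plan, which is not among the documents. But the criterion is fixed in the SAP, and a convention that changed it would contradict Table 3. Version lag does not explain the gap: the SAP was written for the May 2019 protocol, and the current protocol's summary of changes lists no change to Appendix D.

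**The SAP uses what is collected.** The postdose TLS panel has no albumin, and ionized calcium is not a listed test. Predose albumin applied to samples drawn during intravenous hydration is an approximation. This stands as a limitation, but the approximation is closer to Appendix D than no correction. Appendix E also triggers on plain calcium, but that is a management rule, and it too calls for corrected calcium when albumin is low.

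**Other outputs help.** SAP 7.3 also plans listings for subjects with Grade 3 to 4 chemistry values. These are selected by toxicity grade, not by the TLS rule, and the SAP does not say they will set albumin beside calcium.

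**Stronger readings that the documents do not support.**
- A reader might infer that the open-ended window is an error. Protocol 6.2 requires TLS sampling at the optional 600 mg step, so an any-time post-baseline count is defensible. Appendix D itself leaves the start day and the unit unstated. Only the label is at fault.
- A reader might infer that the SAP inflates the rate. Calcium can go either way with albumin. The late end of the window can only add cases, but the post-baseline condition drops pre-therapy abnormalities that Appendix D would count.
- A reader might infer that a delayed ramp-up reclassifies subjects. A 3-day hold moves the 400 mg step from Day 5 to Day 8 and its 24-hour draw to Day 9, outside the window. But the measure is per subject, and someone held for laboratory TLS inside the window is already counted under both rules.

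**Conclusion.** The calcium criterion in SAP Table 3 is not the one in Protocol Appendix D, although both are called Howard. This is certain from the text. The cut-off differs by 0.8 mg/dL of measured calcium for each 1 g/dL of albumin away from 4.

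Whether any subject's status will change is not known. It needs one other abnormal analyte in the same 24 hours, a measured calcium between the two cut-offs, and no ionized calcium result that gives the same status under both rules. The number could be zero, and the net direction cannot be stated.

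The point is minor. It touches one descriptive table and its listing. SAP 7.2 counts TLS adverse events separately by a standardized MedDRA query, and neither the response rate nor the futility rule is affected. The window difference is secondary: a matter of labelling, resting on reading the unprinted unit as days.

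**What to change.** In SAP 7.3:

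1. In Table 3, replace calcium with albumin-corrected calcium by the Appendix D formula, or ionized calcium below the Appendix D limit where a site measured it. Apply the nearest predose albumin to postdose TLS panels without albumin, and state that this is an approximation during intravenous hydration. Add albumin to the listing.
2. Keep the any-time post-baseline count, labelled as wider than the Appendix D window. Beside it, show post-baseline events up to 7 days after one named start day. Do not add pre-drug abnormalities to the on-treatment rate.
3. Editorial: the first summary bullet should cite Table 3, since Table 4 holds the vital signs limits. It should also require at least two different analytes, because two values could be read as one analyte measured twice.

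The cost is a few lines of SAP text and some programming, including the albumin rule. No visit or sample is added, because albumin is already in the predose full chemistry panel. Ionized calcium can be used only where a site happened to measure it.

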7.4 Analysis of Vital Signs

For selected vital signs variables, a listing of all observations collected (at both scheduled and unscheduled visits) will be generated for subjects that had at least one post-baseline observation meeting pre-defined criteria for potentially clinically significant values. The number and percentage of subjects who have at least one post-baseline observation

meeting the pre-defined criteria for potentially clinically significant values will be provided for each variable.

Pre-defined criteria for potentially clinically significant vital signs values are given in [Table 4](#):

Table 4. Criteria for Potentially Clinically Significant Vital Signs – Vital Signs Variables

Vital Signs Variables	Criterion	Definition of Potentially Clinically Significant
Systolic blood pressure	High	Value \geq 160 mmHg
Diastolic blood pressure	High	Value \geq 100 mmHg
Heart rate	Low	Value $<$ 50 bpm
	High	Value \geq 120 bpm
Temperature	Low	Value $<$ 36°C
	High	Value \geq 38.5°C

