Such an event can result from use of the drug as stipulated in the protocol or labeling, as well as from "special situations," such as accidental or intentional overdose, medication error, occupational or accidental exposure, off-label use, drug abuse, drug misuse, or drug withdrawal, all which must be reported whether associated with an AE or not. Any worsening of a pre-existing condition or illness is considered an AE. Worsening in severity of a reported AE should be reported as a new AE. Laboratory abnormalities and changes in vital signs are considered to be AEs only if they result in discontinuation from the study, necessitate therapeutic medical intervention, meets protocol-specific criteria (see Section 6.2 regarding toxicity management), and/or if the investigator considers them to be AEs.

The investigators will monitor each subject for clinical and laboratory evidence of AEs on a routine basis throughout the study. All AEs will be followed to a satisfactory conclusion.

An elective surgery/procedure scheduled to occur during a study will not be considered an AE if the surgery/procedure is being performed for a pre-existing condition and the surgery/procedure has been preplanned prior to study entry. However, if the pre-existing condition deteriorates unexpectedly during the study (e.g., surgery performed earlier than planned), then the deterioration of the condition for which the elective surgery/procedure is being done will be considered an AE.

If an AE, whether associated with study drug or not, meets any of the following criteria, it is to be reported to AbbVie clinical pharmacovigilance or contract research organization (as appropriate) as an SAE within 24 hours of the site being made aware of the SAE (refer to the Operations Manual Section 4.3 for reporting details and contact information):

Death of Subject	An event that results in the death of a subject.
Life-Threatening	An event that, in the opinion of the investigator, would have resulted in immediate fatality if medical intervention had not been taken. This does not include an event that would have been fatal if it had occurred in a more severe form.
Hospitalization or Prolongation of Hospitalization	An event that results in an admission to the hospital for any length of time or prolongs the subject's hospital stay. This does not include an emergency room visit or admission to an outpatient facility.

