7.5 Statistical Analyses for Safety

The safety and tolerability will be assessed by evaluation of study drug exposure, AEs, SAEs, and deaths as well as changes in laboratory measurements, physical examinations, and vital sign parameters.

Statistical analyses for safety are described and fully documented in the SAP.

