 Spleen and lymph node measurements will be performed during the physical examination or via ultrasound in addition to CT scan to have baseline data for the upcoming clinical disease assessments.
 CT scan will be accepted for screening purposes if previously performed within 35 days before the first dose of study drug.
 Cheek swab and blood sample for optional biomarker assessments (if consent was given for the correlative studies) may be performed once any time from Day –28 to Day –2.

Days -3 and -2:

 INTERVIEW	Adverse event assessment	
 EXAMINATION	Physical examination (Day -3 to Day -1)	Weight (Day -3 to Day -1)
 LABORATORY	Computed tomography (Day -28 through Day -2) Cheek swab (Day -28 to Day -2)	Blood sample for optional biomarker assessment (Day -28 to Day -2)
 TREATMENT	Dispense venetoclax and ibrutinib	Oral hydration Oral antihyperuricemic agent

NOTES: All Days -3 and -2 procedures must be performed onsite.
 A sign- and symptom-directed physical examination and weight may be performed any time from Day -3 to Day -1.
 CT scan will be accepted for screening purposes if previously performed within 35 days before the first dose of study drug.
 Cheek swab and blood sample for optional biomarker assessments (if consent was given for the correlative studies) may be performed once any time from Day -28 to Day -2.
 Electronic transaction for dispensation of venetoclax and ibrutinib can be performed within 3 days of the first dose of study drug (Day -1).

Day -1:

 INTERVIEW	Adverse event assessment	Prior/concomitant therapy
 EXAMINATION	Physical examination (Day -3 to Day -1)	Weight (Day -3 to Day -1) Vital signs
 LABORATORY	Urine pregnancy test Hematology/chemistry sample (predose)	Blood sample for optional biomarker assessments
 TREATMENT	Dispense venetoclax and ibrutinib Hospitalization	Intravenous hydration Ibrutinib dosing

NOTES: All Day -1 procedures must be performed onsite.
 A sign- and symptom-directed physical examination and weight may be performed any time from Day -3 to Day -1.
 Ibrutinib dosing occurs once daily until end of treatment.
 Electronic transaction for dispensation of venetoclax and ibrutinib can be performed within 3 days of the first dose of study drug (Day -1).
 Blood sample for biomarker optional assessments will be collected at predose and 6 hours postdose for subjects who provided consent for the correlative studies.

Week 1, Days 1 through 5:

 INTERVIEW	Adverse event assessment Concomitant therapy	

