3.18 Dispense Study Drug

Study drug will be dispensed to subjects as specified in Section 2.1. The first dose of study drug will be administered after all other baseline (Day –1) procedures are completed. At the visits specified in Section 2.1, the site personnel will review and retain a copy of the dosing diary, review returned study drug kits, and empty study drug packaging to verify compliance.

Dosing Instructions and Dosing Card

Subjects will be provided with self-administration dosing instructions and a study drug dosing diary at visits noted in Section 2.1. Subjects will be instructed to record the exact date, time (to the nearest minute), and number of tablets and capsules of the last 2 doses of venetoclax and ibrutinib, respectively, taken prior to each scheduled PK sample collection as noted in Section 2.1. Subjects should be instructed to complete the dosing diary at the time the doses are taken. Site personnel will collect the completed dosing diaries from all subjects at the visits indicated in Section 2.1. The information from the study drug dosing diary will be recorded in the eCRF. In the event that the dosing diary is not available, the site may obtain dosing information via subject interview and record this information in the eCRF and the subject's source documents.

To facilitate proper dosing of study drug before PK blood samples are taken, the following procedures should be performed:

- Site personnel will contact the subject approximately 2 days prior to the scheduled visit date to review the importance of properly documenting dosing information (specifically, the date and time of the last 2 doses prior to the visit where the PK sample is drawn) onto the dosing diary and remind the subject to bring the completed dosing diary to the scheduled study visit. The date and time of the contact will be recorded in the subject's source documents.
- The completed dosing diary will be collected by site personnel on the day of the visit and kept as a source record of dosage administration times documented in the eCRF.

COVID-19 Pandemic-Related Acceptable Protocol Modifications

Study drug may be shipped from the study site directly to the study subject's home if all the following criteria are met:

- Direct-to-patient (DTP) shipment of study drug is allowed by local regulations and the relevant ethics committee
- Study drug can be administered by the subject (or subject's caregiver) at home

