7.2 Analysis of Adverse Events

All summaries/analyses involving AEs will include treatment-emergent adverse events (TEAE) only, unless otherwise specified. TEAE are defined as any event with onset after the first dose of study drug and no more than 30 days after the last dose of study drug. Events where the onset date is the same as the study drug start date are assumed to be treatment-emergent, unless the study drug start time and the AE start time are collected and the AE start time is prior to the study drug start time. If an incomplete onset date was collected for an AE, the AE will be assumed to be treatment-emergent unless there is evidence that confirms that the AE was not treatment-emergent (e.g., the AE end date was prior to the date of the first dose of study drug).

For summaries of AEs related (reasonable possibility) to study drug, at each level of summation (overall, SOC, and PT) each subject is counted only once. If a subject has an AE with unknown relationship, then the subject will be counted in the relationship category of "unknown," even if the subject has another occurrence of the same event with a relationship of "no reasonable possibility" present. The only exception is if the subject has another occurrence of the same AE with the relationship of "reasonable possibility." In this case, the subject will be counted under the reasonable possibility category.

Adverse event data will be summarized and presented using primary MedDRA system organ classes (SOCs) and preferred terms (PTs) according to the MedDRA coding dictionary version 21.0 or higher.

The number and percentage of subjects experiencing treatment-emergent adverse events will be summarized for the following adverse event summaries:

- Any treatment-emergent adverse event.
- Any treatment-emergent adverse event with NCI toxicity (CTCAE version 5.0) grade 3, 4, or 5 adverse events.
- Any treatment-emergent adverse event with NCI toxicity (CTCAE version 5.0) grade 3 or 4 adverse event.
- Adverse events broken down by NCI toxicity grade (Severity).
- Any treatment-emergent serious adverse event.
- Any treatment-emergent adverse event leading to discontinuation of venetoclax.
- Any treatment-emergent adverse event leading to venetoclax interruption.
- Any treatment-emergent adverse event leading to venetoclax reduction.
- Any treatment-emergent adverse event that is rated at least possibly related to venetoclax by the investigator (Reasonable Possibility Related)

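### SAP 7.4 reports vital signs only as the share of subjects ever past a fixed threshold, so values already high at baseline, off-drug readings and new on-treatment onsets are counted together

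*SAP*

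**What the plan says.** SAP 7.4 plans two outputs for selected vital signs. One is a count: "The number and percentage of subjects who have at least one post-baseline observation" meeting a Table 4 criterion, per variable. The other is a listing of every observation for the subjects so flagged. The Table 4 criteria are absolute levels: systolic pressure at or above 160 mmHg, diastolic at or above 100 mmHg, and limits for heart rate and temperature. SAP 7.4 has no change from baseline, no split by baseline status and no definition of baseline for vital signs.

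SAP 7.1 and Protocol 3.4 set the period for safety as the whole study.

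Protocol 7.5 says that safety will be assessed by, among other things, "changes in laboratory measurements, physical examinations, and vital sign parameters". Protocol 6.2 lists the known potential risks of ibrutinib as "hemorrhage, infections, cytopenias, cardiac arrhythmias, hypertension, second primary malignancies, and TLS".

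Other parts of the SAP are more specific. SAP 7.2 limits treatment-emergent events to "onset after the first dose of study drug and no more than 30 days after the last dose of study drug". The laboratory grade shifts in SAP 7.3 cross-tabulate baseline grade against later grade and stop at 30 days after last dose.

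Vital signs are also collected at the post-treatment follow-up visits, which run until progression or another therapy (Operations Manual 2.2).

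**The concern.** With no control arm, the subject's own baseline is the only internal reference for a blood-pressure effect. A count of anyone ever past 160/100 mmHg does not use it. The eligibility criteria in Protocol 5.1 set no numeric blood-pressure limit, so a subject can enter at or near the threshold and be counted later with no change at all. A subject whose only high reading comes months after stopping both drugs is counted in the same way. A reader of the safety table could not tell from the percentage how many subjects newly crossed the threshold on treatment.

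At stake is how clearly the report describes a named risk. No efficacy result or design decision is involved.

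**Working it through.** SAP 7.4 states no numerical target for vital signs, so there is no figure of the plan's to reproduce. The check compares passages and adds simple arithmetic.

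**1. Is a baseline comparison available elsewhere?** SAP 7.1 adds only that vital signs will be analysed as appropriate. SAP Table 2 (selected adverse events) does not include hypertension. Laboratory grades get a baseline-by-later shift table in SAP 7.3. Vital signs get none.

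**2. Can off-drug readings enter the count?** Yes. The scope is the whole study, and Operations Manual 2.2 lists vital signs at the 30-day visit (held no earlier than 30 days after last dose) and at post-treatment visits. This affects only subjects who stop without progression and have not started another therapy. The SAP was written for the protocol dated 02 May 2019. Protocol Appendix H shows that the post-treatment visits, and the endpoints now listed in Protocol 7.5, were added in the later amendment. The mismatch is therefore largely a matter of version lag.

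**3. Which value is baseline?** Ibrutinib starts on Day -1. Operations Manual 3.18 says "The first dose of study drug will be administered after all other baseline" procedures on Day -1 are complete, and the Day -1 visit notes also tie the first dose to that day: "Electronic transaction for dispensation of venetoclax and ibrutinib can be performed within 3 days of the first dose of study drug" (Day -1). The pre-ibrutinib Day -1 value is the natural baseline, but SAP 7.4 does not say so. SAP 7.3, for laboratory values, has two rules. For subjects not hospitalised, "the baseline value will be the 0 hour lab draw prior to the first dose of study drug on Day 1". For hospitalised subjects, it places admission on the day before first dose. Protocol 6.2 has admission one day before venetoclax, which is the day ibrutinib starts. Both rules therefore treat Day 1 as the first dose.

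**4. Weight of one subject.** If all enrolled subjects are dosed, one subject contributes 1/n:

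- n = 37 (maximum enrolment): 1/37 = 2.7 points
- n = 31 (relapsed or refractory total after 7 or more Stage 1 responders): 1/31 = 3.2 points
- n = 14 (stop after Stage 1): 1/14 = 7.1 points

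**5. How the mixing works (illustration, assumed inputs).** Let f be the share past the threshold at baseline, all flagged again later, and t the new-onset rate in the rest. The reported share is f + (1 - f)t. With t = 10% and n = 37:

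| f | Flagged, 37 × (f + (1 - f)t) | New onsets, 37 × (1 - f)t |
|---|---|---|
| 5% | 5.4 | 3.5 |
| 10% | 7.0 | 3.3 |
| 20% | 10.4 | 3.0 |

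The reported count rises as the number of new onsets falls.

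**6. Level against change (illustration, assumed inputs).** Take 11 reading days to Week 24 (Week 1 Days 1 to 6; Weeks 4, 8, 12, 16 and 24), independent normal readings and a within-subject SD of 5, 8 or 10 mmHg. The documents give no SD. The chance of a systolic flag is 1 - Φ((160 - mean)/SD)^11. At an on-treatment mean of 150 it is 22%, 71% and 85%, whether the subject began at 150 or rose from 130. A rise from 120 to 140 goes unflagged with probability Φ(20/SD)^11, which is 99.97%, 93% and 78%. These figures show how the statistic behaves. They do not estimate the size of the problem in this trial.

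**The case against.** The strongest reply is that a threshold count with a full listing is a workable summary for at most 37 subjects in a study that SAP 4.6 calls hypothesis generating. The listing shows every reading for each flagged subject, so a reader can classify each one by hand. That stands, and it limits the point to the summary percentage. It does not help for subjects who were never flagged, because they are not listed.

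Three stronger readings are tempting, and the documents do not support them.

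- **That the SAP forgot to end the window.** SAP 7.1 and Protocol 3.4 both state whole-study scope, and the liver-threshold count in SAP 7.3 has no end date either. The open period is a stated choice. The point is that a single count over that period is hard to interpret.
- **That baseline will be taken after ibrutinib.** The Day 1 rule is for laboratory values in subjects not hospitalised, and Protocol 6.2 hospitalises everyone. SAP 5.1 and 7.1 define study drug as either agent. The companion rule for hospitalised subjects is loosely worded, so one clarifying sentence is worthwhile, but it is secondary.
- **That blood-pressure rises below threshold will go unseen.** Protocol 6.1 says "Laboratory abnormalities and changes in vital signs are considered to be AEs only if they result in discontinuation from the study", but the sentence goes on to include changes that need therapeutic intervention, meet protocol-specific criteria or are considered adverse events by the investigator. These reach the treatment-emergent tables. SAP 7.1 allows further analysis as appropriate, and the Statistical Programming Plan, which is not among the documents, may add conventions. The gap left in the stated outputs is an untreated rise below threshold that nobody reported.

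It can also be said that the word for changes in Protocol 7.5 is generic, since it covers physical examinations too, and that the protocol leaves the method to the SAP. That is fair. It weakens any claim of a formal contradiction, but SAP 7.4 still summarises no change.

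**Conclusion.** The point holds as a small, inexpensive improvement to descriptive safety reporting. The SAP 7.4 percentage combines thresholds met at baseline, off-drug readings and on-treatment onsets, and no change in vital signs is summarised although Protocol 7.5 says change will be assessed. The only size that follows from the documents is the weight per subject: 2.7 points at 37, 3.2 at 31 and 7.1 at 14, assuming all enrolled subjects are dosed. How many subjects would be affected is unknown. The illustrations depend on assumed SDs, means and rates, and a reader should not take them as evidence of how large the defect is. The primary endpoint and the stage decision do not depend on any of this.

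**What to change.** Add wording to SAP 7.4 along these lines:

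> Baseline is the last vital-signs value before the first dose of either study drug, that is, before ibrutinib on Day -1. Subjects meeting each Table 4 criterion will be shown by whether they met it at baseline. Counts will be given for values up to 30 days after the last dose of study drug and, alongside, for the whole study. Systolic and diastolic change from baseline will be summarised by visit, with the number assessed. Values later than 30 days after last dose will be marked in the listing.

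The 30-day limit matches SAP 7.2 and the grade shifts in SAP 7.3. Keeping the whole-study count means that no reading is dropped.

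The cost is SAP wording and one or two descriptive tables from data already collected. There are three limits. Most readings from the 30-day visit will fall outside the windowed count, because that visit is held no earlier than day 30. Off-drug readings within the 30 days remain in it. Week 1 changes need care because subjects receive intravenous hydration in hospital, and later visits need care because fewer subjects will be assessed.
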